3.5.2. Laboratory Data

Below is a list of hematology and serum chemistry test parameters.

- Hematology: hemoglobin, hematocrit, red blood cell count, reticulocyte count, platelet count, white blood cell count with differential, total neutrophils, eosinophils, monocytes, basophils, lymphocytes, coagulation panel.
- Serum chemistry: blood urea nitrogen, creatinine, creatine phosphokinase, glucose, sodium, potassium, chloride, calcium, total bicarbonate, aspartate aminotransferase, alanine aminotransferase, gamma-glutamyl transferase, bilirubin, alkaline phosphatase, lactate dehydrogenase, uric acid, albumin, total protein, total cholesterol, low-density lipoprotein (LDL), high-density lipoprotein (HDL), triglycerides.

3.5.3. Vital Signs, including Height and Weight

Vital sign measurements are oral or tympanic temperature, respiratory rate, pulse rate and blood pressures.

Height and weight are collected at pre- and post-treatment.

3.5.4. Physical Examinations

Complete physical examinations consist of assessments of general appearance; skin; head, eyes, ears, nose and throat; mouth, heart; lungs; breast (optional); abdomen; external genitalia (optional); extremities; neurologic function; and lymph nodes.

4. ANALYSIS SETS

Data for all subjects will be assessed to determine if subjects meet the criteria for inclusion in each analysis population described below prior to unblinding and releasing the database and classifications will be documented per standard operating procedures.

4.1. Full Analysis Set

The Full Analysis Set (FAS) is defined as all subjects who have been randomized and who have received at least one dose of treatment. Subject is assigned to the randomized treatment group regardless of actual treatment received. Analyses for endpoints that are defined based on a threshold of change from baseline (eg, NRS4) will also require the baseline value to be equal to or greater than that threshold (eg, for NRS4, the baseline value needs to be ≥ 4).

It is expected that the FAS as defined here will be identical to an ITT analysis set (randomized and dispensed study medication) because the first dose is administered in-clinic. The number of subjects randomized and dispensed study medication but did not receive treatment will be reported.

4.2. Per Protocol Analysis Set

The Per Protocol Analysis Set (PPAS) is defined as a subset of FAS who had no major protocol violations. The subjects excluded from the PPAS will be determined and documented before the study is unblinded. The primary and key secondary endpoints will be analyzed for the PPAS. This set will include subjects who:

- Were eligible for the study by way of meeting key inclusion criteria and none of the key exclusion criteria.
- Had valid and non-missing baseline efficacy data (IGA and EASI score).
- Had actual, observed IGA and EASI scores at Visit 8 / Week 12.
- Did not take a protocol-prohibited medication for the primary diagnosis prior to completion of the study dosing period (Visit 8 / Week 12).
- Took the correct randomized treatment for at least 80% and at most 120% of the assigned amount until completion of the study dosing period (Visit 8 / Week 12).
- Had no other major protocol violations as determined by the clinical team prior to database lock. A major protocol violation in this context is one that is likely to affect materially the efficacy responses of the patient and will be defined by the clinical team before database is locked and any analysis is performed for this study.

These items will either be assessed by programmed checks of the data or be determined by clinical review prior to unblinding of study treatment.

4.3. Safety Analysis Set

The Safety Analysis Set (SAF) will be defined as all subjects who receive at least one dose of study medication classified according to actual study treatment received. The safety analysis set is the primary population for treatment administration / compliance and safety. A randomized but not treated subject will be excluded from the safety analyses.

5. GENERAL METHODOLOGY AND CONVENTIONS

The final analysis and reporting of results will be performed after the completion of the study and the database is locked.

5.1. Hypotheses and Decision Rules

PF-04965842 200 mg QD will be declared superior to placebo if the null hypothesis of no difference between PF-04965842 200 mg QD versus placebo for **both** co-primary endpoints is rejected at the 5% significance level. Similarly, PF-04965842 100 mg QD will be declared superior to placebo if the null hypothesis of no difference between PF-04965842 100 mg QD versus placebo for **both** co-primary endpoints is rejected at the significance level specified below.

[figure not shown]
A sequential Bonferroni-based iterative multiple testing procedure to strongly control the familywise Type 1 error at 5% will be used for testing each of the two PF-04965842 doses (200 mg QD and 100 mg QD) versus placebo on the primary and key secondary endpoints. The procedure belongs to a class of consonant multiple test procedures ([Hommel et al. 2007](#)) which are a subclass of the closed test procedures ([Marcus et al. 1976](#)).

The procedure will first test the Week 12 co-primary endpoints (IGA and EASI-75) for 200 mg QD vs placebo at a 5% significant level. If this hypothesis is not rejected, then no further testing will be conducted. If this hypothesis is rejected, then testing may continue on

two paths depending on the testing for Week 2 NRS4 for severity for 200 mg QD vs placebo at a 2.5% significance level:

- If the hypothesis for the Week 2 NRS4 for severity for 200 mg QD vs placebo is rejected, then the unused alpha level of 2.5% will be passed on to a series of testing in Sequence A (see Figure 2 below) at a 5% significance level. If any hypothesis in this sequence is not rejected, then the procedure stops.
- If the hypothesis for the Week 2 NRS4 for severity for 200 mg QD vs placebo is not rejected, then the series of testing in Sequence A (see Figure 2 below) will be tested at a 2.5% significance level. If any hypothesis in this sequence is not rejected, then the procedure stops. If all hypotheses in this sequence are rejected, then the unused alpha level of 2.5% will be passed on to the testing of hypotheses for Week 2 NRS4 for severity (200 mg QD vs placebo) at a 5% significance level.

Figure 2 Schematic for Multiple Testing Procedure

Hypotheses for all other endpoints not described here are to be tested at the nominal 5% significant level, without making adjustments for multiple comparisons.

090177e1912f28b6\Approved\Approved On: 26-Jun-2019 09:22 (GMT)

5.2. General Methods

In general, for descriptive analyses, number and percent will be presented for binary endpoints. Number, median, Q1 and Q3 will be presented for descriptive analyses of continuous efficacy endpoints.

5.2.1. Analyses of Binary Data

Binary data at each scheduled visit will be analyzed by two approaches: (1) the test of hypothesis (and the p-value) between the PF-04965842 treatment groups versus the placebo group will be conducted by the Cochran-Mantel-Haenszel (CMH) statistic adjusting for the effect of randomization strata; p-values from the CMH statistic will be used to establish the superiority of each dose of PF-04965842 to placebo in binary responses; and (2) the proportion of responders in the PF-04965842 treatment groups versus the placebo group will be summarized by the difference and its 95% confidence interval obtained by normal approximation. The difference in proportions will be calculated within each randomization stratum. The final estimate of the difference in proportions will be a weighted average of these stratum-specific estimates using CMH weights. The CMH weight w_k for stratum k ($k = 1, 2, 3, 4$) is given by,

$$w_k = \frac{\frac{n_{ik} n_{ck}}{n_{ik} + n_{ck}}}{\sum_{j=1}^4 \frac{n_{ij} n_{cj}}{n_{ij} + n_{cj}}}$$

where n refers to sample size, the subscript c refers to a comparator group (e.g., placebo) and the subscript i refers to a test group (e.g., either the low or high doses; so that two test statistics are calculated, one for each dose versus placebo). The difference is estimated as $\hat{d} = \sum_{k=1}^4 w_k (\hat{p}_{ik} - \hat{p}_{ck})$, where \hat{p} refers to the estimated relative frequency. An estimate for \hat{p} is obtained as x/n , where x is the number of responders.

Two-sided 95% confidence intervals for the difference (based on a normal approximation) are formed by:

$$\hat{d} \pm 1.96 \sqrt{\sum_{k=1}^4 w_k^2 \left(\frac{\hat{p}_{ik}(1 - \hat{p}_{ik})}{n_{ik}} + \frac{\hat{p}_{ck}(1 - \hat{p}_{ck})}{n_{ck}} \right)}$$

In the above formula for the variance of \hat{d} (under the square-root sign), when the number of responders is zero ($x = 0$), then \hat{p} will be replaced by $0.5/(n + 1)$. This change will be made only for calculating the variance of \hat{d} and not anywhere else. Estimates of the difference in proportions along with the two-sided 95% confidence interval will also be provided for the PF-04965842 200 mg QD group versus the PF-04965842 100 mg QD group. No hypotheses will be tested.

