9.2.3. Analysis of the Primary Endpoints

The co-primary endpoints will be analyzed using the (Cochran-Mantel-Haenszel) test adjusted by randomization strata (baseline disease severity and age) and both must achieve statistical significance to meet the primary objective. The difference between each active group and the placebo group in the proportion of subjects achieving IGA response (similarly for EASI75) along with its 95% confidence interval (using the normal approximation for the difference in binomial proportions) will be reported. If a subject withdraws from the study, then this subject will be counted as non-responder for endpoints after withdrawal. Additional secondary analyses will utilize missing at random (MAR) and missing not at random (MNAR) approaches (eg, longitudinal mixed models and jump to reference analyses).

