Sample size for the study was based on the co-primary endpoints. A sample of 150 subjects randomized to PF-04965842 200 mg QD, 150 subjects randomized to PF-04965842 100 mg QD and 75 subjects randomized to placebo would provide at least 95% power to detect a difference in IGA response rate of at least 20% between PF-04965842 200 mg QD (or PF-04965842 100 mg QD) and placebo, assuming the placebo response rate is 6% at Week 12. Furthermore, this will also provide at least 99% power to detect a difference in EASI-75 response rate of at least 30% between PF-04965842 200 mg QD (or PF-04965842 100 mg QD) and placebo, assuming the placebo response rate is 15% at Week 12.

The Type-I error for testing each individual co-primary endpoint was set at 5%. Since both endpoints are co-primary, the study will meet its primary endpoint only if both hypotheses (corresponding to each co-primary endpoint) are rejected. Therefore, the Type-I error rate remains controlled at 5% for testing the primary endpoints. The power to reject both hypotheses when a true difference exists (alternative hypothesis is true) could be at least 94% depending on the correlation between the endpoints.

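### The reported 95% interval for the co-primary differences uses a different variance from the CMH test, so it can exclude zero when the test fails, almost always in the drug's favour

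*SAP*

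**What the plan says.** SAP 5.2.1 gives the test and the interval separate roles. On the test: "p-values from the CMH statistic will be used to establish the superiority of each dose of PF-04965842 to placebo in binary responses". The size of the effect "will be summarized by the difference and its 95% confidence interval obtained by normal approximation". The point estimate weights the stratum differences by the CMH weights w_k. The interval formula is introduced with the words "Two-sided 95% confidence intervals for the difference (based on a normal approximation". Its variance is built from each arm's own p(1−p)/n, and a zero count is replaced by 0.5/(n+1) in that variance only. Protocol 9.2.3 has the same pairing: a CMH test for the co-primary endpoints, and the difference "along with its 95% confidence interval (using the normal approximation for the difference in binomial proportions) will be reported".

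The decision rule in SAP 5.1 refers to hypothesis tests only. The 200 mg dose is superior if the null for both "co-primary endpoints is rejected at the 5% significance level". Neither document says that the interval and the test can disagree, or how to report it if they do.

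**The concern.** The interval is the effect estimate that readers of the report will see beside the primary p-value. If a dose does less well than planned, the report could show an interval wholly above zero next to a failed co-primary test. Because both co-primaries must succeed for a dose, such a result would sit at the centre of the report, and the plan gives no guidance on reading it. The disagreement runs almost entirely in one direction, so near-95% two-sided coverage does not reveal it.

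**Working it through.** **Inputs.** SAP 2.2: 150 subjects per dose and 75 on placebo; planning rates 6% against 26% (IGA) and 15% against 45% (EASI-75); four strata (severity by age). Stratum sizes are not given. Assumed here: 72/48/18/12 active and 36/24/9/6 placebo, response in moderate disease twice that in severe, and CMH without continuity correction.

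**The plan's own figures.** With a null standard error for the critical value and an unpooled one for the alternative:
- IGA: pooled rate (2×0.26+0.06)/3 = 0.193, null SE 0.056, unpooled SE 0.045, power 97.8%.
- EASI-75: pooled rate 0.35, null SE 0.067, unpooled SE 0.058, power 99.8%.
- Jointly, 0.95 × 0.99 = 94.05%.

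The stated minimums of 95%, 99% and 94% hold.

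**Where test and interval part.** Write m_k for responders and N_k for subjects in stratum k. Since w_k is proportional to n_ik·n_ck/N_k, the weighted difference is proportional to the CMH numerator. Only the variance differs:
- CMH, per stratum: n_ik·n_ck·m_k(N_k−m_k)/[N_k²(N_k−1)].
- SAP interval, per stratum: w_k²[p_ik(1−p_ik)/n_ik + p_ck(1−p_ck)/n_ck].

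**Size of the gap, unstratified.** At 15% against 6%, the unpooled SE is √(0.15×0.85/150 + 0.06×0.94/75) = 0.0400. The pooled SE, with rate 0.12, is √(0.12×0.88×(1/150+1/75)) = 0.0460. The unpooled SE is 13% smaller because the low-variance arm is also the small arm.

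**One result by hand: 23/150 against 5/75.**
- Difference 8.67 points. SE = √(0.1533×0.8467/150 + 0.0667×0.9333/75) = 0.0412. Interval 8.67 ± 1.96×4.12 = 0.6 to 16.7 points.
- CMH: expected 150×28/225 = 18.67, variance 150×75×28×197/(225²×224) = 5.472, chi-square (23−18.67)²/5.472 = 3.43, p = 0.064.
- With these counts spread over the assumed strata: SAP interval 0.5 to 16.9, CMH p = 0.065, stratified score interval −0.6 to 16.6.

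**All 151 × 76 = 11,476 unstratified tables.** With pooled response below 50%, 40 tables have an interval excluding zero with CMH p > 0.05, and all 40 favour the drug. In 25 tables CMH rejects while the interval includes zero, and all 25 favour placebo. At 112 against 112 the interval-only disagreement was at most 0.9% in the settings tried, and it was symmetric under the null, so the 2:1 ratio drives the direction.

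**Simulated frequency** (100,000 trials per setting, SAP formula with the zero-count rule):

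| Endpoint (placebo rate) | Active rate | Interval above zero, CMH p > 0.05 |
|---|---|---|
| IGA (6%) | 12% | 8.3% |
| | 15% | 8.4% |
| | 18% | 6.1% |
| | 20% | 4.3% |
| | 26% (planning) | 0.6% |
| EASI-75 (15%) | 25% | 6.2% |
| | 30% | 4.6% |
| | 35% | 1.8% |
| | 45% (planning) | 0.06% |

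A repeat with 200,000 trials per setting agreed within about 0.1 point. The opposite disagreement was about 0.01% or less when the drug works.

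**Misses by tail (nominal 2.5% each).** EASI-75: lower limit 3.2–3.4%, upper about 2.1–2.2%. IGA with an effective drug: lower 2.5–2.6%, upper about 1.7–2.1%.

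**The alternative interval.** At a difference of zero, the Miettinen-Nurminen constrained rates both equal m_k/N_k. With the N_k/(N_k−1) factor its variance becomes the CMH expression above. It disagreed with CMH in no simulated trial. Its lower limit missed in about 1.9–2.3% of trials and its upper in about 2.3–2.7%.

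**The case against.** The strongest reply is that nothing is decided by the interval. The CMH p-value establishes superiority, the Wald interval was prespecified in both documents, and a null-variance test beside an unpooled interval is common practice. That stands. A reader might infer that the false-positive risk is inflated; the documents do not support this, because no claim rests on the interval.

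The second reply is that the disagreement is rare where the trial expects to be: 0.6% and 0.06% at the planning rates, and 0.4% and 0.0% at the Phase 2b IGA rates in Protocol 1.2.4 (27.8% and 44.5% against 6.3%). That also stands. The issue matters for a dose with a smaller effect, roughly 6 to 15 points.

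Third, a reader might infer that the SAP's lower limits are generally too optimistic. For IGA, where disagreement is most frequent, the lower limit is near nominal, so that disagreement mainly reflects a conservative CMH test. Only for EASI-75 is the lower tail itself off.

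Fourth, a reader might expect a matched interval to end every contradiction. It cannot. Protocol 9.2.2 places the 100 mg co-primaries in Sequence A, which is tested at 2.5% if the Week 2 NRS4 hypothesis for 200 mg is not rejected. In that branch any 95% interval matched to CMH still excludes zero when p lies between 0.025 and 0.05. That is about 13.6% of trials at IGA 15% against 6% and 11.2% at EASI-75 30% against 15%.

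Finally, the Wald standard error cannot simply be deleted. SAP 5.3.1 and Appendix 3 feed it into Rubin's rules for the tipping-point and NRS4 analyses.

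**Conclusion.** The concern holds as a reporting inconsistency, and correcting it is a cheap improvement. The co-primary interval is not matched to the co-primary test, and under 2:1 allocation with response below 50% the mismatch favours the drug almost without exception. It affects about 8% of trials at IGA 12–15% against 6% and 5–6% at EASI-75 25–30% against 15%, but well under 1% at the planning rates. The superiority decision, its type I error and its power do not change.

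The frequencies rest on assumed stratum sizes and an assumed severity ratio. The direction was the same under every stratum assumption tried; it would reverse if pooled response exceeded 50%, which is outside the planning rates.

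**What to change.** Before unblinding:

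- For binary analyses without multiple imputation (SAP 5.2.1, 6.1.1 and 6.2.1, with Protocol 9.2.3 reworded to match), keep the CMH test and the CMH-weighted estimate. Report a stratified Miettinen-Nurminen score interval with the same w_k and the N/(N−1) factor. The 95% interval then excludes zero exactly when CMH p < 0.05, and the 0.5/(n+1) rule is not needed for it.
- Keep the Wald variance and the 0.5/(n+1) rule as the standard error for the tipping-point and NRS4 analyses that use Rubin's rules, and say so.
- State that if the 100 mg co-primaries are tested at 2.5%, the 95% interval does not correspond to that test and the CMH p-value governs.

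The cost is wording and a standard software option, with no new data. The lower limit becomes slightly less favourable: in the stratified examples by 1.1 points (0.5 to −0.6 for 23/150 against 5/75) and 0.7 points (10.2 to 9.5 for 39/150 against 5/75). It is also mildly conservative, with the lower limit missing in about 1.9–2.3% of trials.

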6.5.4. Weeks 2, 4, 8 and 12 HADS Response in Adults

- Summaries:
 - Proportion of adult subjects achieving a score < 8 in each of the components (anxiety and depression) of the HADS score at Weeks 2, 4, 8 and 12 (among adult subjects with a score ≥ 8 at baseline);
 - Proportion of adult subjects achieving a score < 11 in each of the components (anxiety and depression) of the HADS score at Weeks 2, 4, 8 and 12 (among adult subjects with a score ≥ 11 at baseline);
- Populations:
 - Adult subjects from the FAS with a baseline corresponding component score ≥ 8 ;
 - Adult subjects from the FAS with a baseline corresponding component score ≥ 11 ;
- Statistical Method: CMH and normal approximation in [Section 5.2.1](#);
- Missing Data: Missing data arising due to subject dropout are considered “non-response” (see [Section 5.3.1](#)).

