6.5.6. Weeks 2, 4, 8 and 12 CDLQI Response in Adolescents

- Summaries:
 - Proportion of adolescent subjects with ≥ 2.5 -point improvement from baseline in the CDLQI score at Weeks 2, 4, 8 and 12 (among adolescent subjects with a score ≥ 2.5 at baseline);
 - Proportion of adolescent subjects with a CDLQI score < 2 at Weeks 2, 4, 8 and 12 (among adolescent subjects with a score ≥ 2 at baseline);
- Populations:
 - Adolescent subjects from the FAS with a baseline CDLQI score ≥ 2.5 ;
 - Adolescent subjects from the FAS with a baseline CDLQI score ≥ 2 ;
- Statistical Method: CMH and normal approximation in [Section 5.2.1](#);

Missing Data: Missing data arising due to subject dropout are considered “non-response” (see [Section 5.3.1](#)).

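### SAP 5.2.1 corrects the variance at 0% response but not at 100%, so the 95% interval is too narrow, or of zero width, when a small cell responds completely

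*SAP*

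**What the plan says.** SAP 5.2.1 works cell by cell: "The difference in proportions will be calculated within each randomization stratum". The four stratum differences (severity by age) are combined with CMH weights. "Two-sided 95% confidence intervals for the difference (based on a normal approximation) are formed by" the weighted difference plus or minus 1.96 times the root of the summed unpooled variances, each of the form p(1−p)/n.

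The estimated proportion is replaced by 0.5/(n + 1) "when the number of responders is zero". The scope is narrow: "This change will be made only for calculating the variance of" the weighted difference. Nothing is said about a cell in which all subjects respond.

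Testing is separate: "p-values from the CMH statistic will be used to establish the superiority of each dose of PF-04965842 to placebo in binary responses". For 200 mg versus 100 mg, 5.2.1 gives the estimate and interval and states that no hypothesis is tested.

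The same method is prescribed for subset endpoints, with no small-sample alternative. SAP 6.5.6 covers adolescents: "improvement from baseline in the CDLQI score at Weeks 2, 4, 8 and 12", in "Adolescent subjects from the FAS with a baseline CDLQI score ≥ 2.5", and also CDLQI below 2. SAP 6.5.4 covers adults who start at or above 8, or at or above 11, and then fall below that cut "in each of the components (anxiety and depression) of the HADS score at Weeks 2, 4, 8 and 12".

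**The concern.** The term p(1−p)/n vanishes at both ends of the scale. The SAP repairs one end only. Two things follow from the text alone, without any assumption about the data. First, the width of the interval depends on whether response or non-response is coded as the event. Second, a full cell is treated as known without error.

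At stake is the reliability of the reported 95% intervals for subset endpoints where cells may be small and response high. Placebo has only 75 subjects in all. Adolescents enter only with sponsor instruction and authority approval (Protocol 3), so their number is not assured. The 200 mg versus 100 mg comparison deserves notice: both arms are active, so high response in both is easier to imagine, and no p-value stands beside the interval.

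**Working it through.** **The plan's own figures.** The plan states no figure for these intervals. The figures it does state on binary endpoints are for power, and they hold up: with 150 versus 75 at two-sided 5%, IGA 26% versus 6% gives 97.8% (96.3% with continuity correction) against the stated 95% or more, and EASI-75 45% versus 15% gives 99.8% (99.7%) against 99% or more. Nothing below depends on them.

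**Variance from one cell.**
- x = 0, n = 4: p = 0.5/5 = 0.1, variance 0.1 × 0.9/4 = 0.0225.
- x = 4, n = 4: p = 1, variance as written 0. With the mirrored value (4.5/5 = 0.9) it is again 0.0225.
- n = 8: 0.00656 at x = 0, and 0 at x = 8 as written.

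**Dependence on coding.** One stratum, 12/12 versus 3/6: variance 0 + 0.25/6 = 0.0417, width 2 × 1.96 × 0.2041 = 0.800. With the active arm at 0/12 instead, the patch adds 0.00308 and the width is 0.829. The size of the difference (0.5) is the same in both.

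**Two strata, 8/8 versus 2/4 and 7/7 versus 3/3.**
- CMH weights: 8×4/12 = 2.667 and 7×3/10 = 2.1, giving 0.559 and 0.441.
- Difference: 0.559 × 0.5 = 0.280.
- As written, only the 2/4 cell contributes: SE = 0.559 × √0.0625 = 0.140, interval 0.006 to 0.554.
- With the mirrored rule: −0.062 to 0.621.

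Here the interval as written excludes zero and the symmetric one does not.

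**Every cell full (8/8 versus 4/4, 7/7 versus 3/3).** As written the interval is 0 to 0. Mirrored it is −0.261 to 0.261, which is what the SAP already gives when every cell is empty.

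**How often a cell fills.** The probability is p to the power n. At p = 0.9 it is 0.73 for n = 3, 0.43 for n = 8 and 0.21 for n = 15. At p = 0.5 and n = 8 it is 0.004.

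**Coverage of the nominal 95% interval (simulation, two severity strata).** Subset sizes and response rates are assumptions, because the documents give neither for these endpoints.

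| Active/placebo | True rates | As written | Symmetric |
|---|---|---|---|
| 10/5 | 0.90 / 0.70 | 78.4% | 92.7% |
| 15/7 | 0.90 / 0.70 | 86.1% | 92.5% |
| 15/7 | 0.95 / 0.60 | 87.0% | 90.5% |
| 15/7 | 0.90 / 0.50 | 88.4% | 91.5% |
| 15/7 | 0.70 / 0.50 | 88.7% | 89.9% |
| 15/7 | 0.70 / 0.30 | 91.0% | 91.8% |
| 15/7 | 0.50 / 0.20 | 93.5% | 93.6% |
| 30/15 | 0.90 / 0.70 | 91.2% | 92.1% |
| 30/15 | 0.95 / 0.60 | 91.0% | 92.6% |

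At 50/25 the two rules differ by at most 0.2 points. With four FAS-size strata at the planning rates for IGA and EASI-75 they agree, with coverage 94.4% to 95.4%.

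The chance that every cell is full, and the interval therefore has zero width, is 0.9^15 × 0.7^7 = 1.7% at 15/7 and 0.9^10 × 0.7^5 = 5.9% at 10/5.

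**200 mg versus 100 mg.** With 15 per arm (9 and 6) at 0.95 versus 0.90, coverage is about 86% as written and 98.6% with the symmetric rule. Zero-width intervals occur with probability 0.95^15 × 0.90^15, about 9.5%.

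**The case against.** The strongest objection is that the effect is conditional and its conditions are undocumented. A reader might infer that intervals for all the subset endpoints are too narrow and cover well below 95%. The documents do not support that. They give no subset sizes and no response rates for CDLQI or HADS, and they allow for no adolescents being enrolled. The largest placebo-comparison losses assume 70% placebo response; the only placebo rates in the plan, for other endpoints, are 6% and 15%. The 10/5 case has placebo cells of 3 and 2 subjects, where any interval of this type is fragile. The stricter target, CDLQI below 2, may well have response too low for cells to fill. All of this stands.

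A reader might also extend the point to DLQI response in adults (SAP 6.5.5), which uses the same formula. Its entry thresholds are baseline scores of at least 2 or at least 4, in subjects with EASI of at least 16, IGA of at least 3 and pruritus NRS of at least 4. Nothing suggests that this subset is small.

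Nor does the missing rule explain all the undercoverage. At 15/7 with rates 0.70 versus 0.50, the symmetric rule recovers 1.2 of the 6.3 missing points; the rest comes from the normal approximation.

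Finally, CMH p-values do not use this variance, and the affected endpoints are additional patient-reported outcomes outside the multiplicity procedure. SAP 5.3.1 does pass these standard errors into Rubin's rules for the imputed analyses, but those concern FAS endpoints; in the FAS-size runs the two rules gave the same coverage.

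What survives is the rule itself. It gives a wrong variance at x = n whatever the data turn out to be.

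**Conclusion.** The point holds in conditional form and is minor. As written, SAP 5.2.1 gives an interval that is too narrow whenever a stratum-by-arm cell has 100% response, and one of zero width when all cells do. That requires small cells together with high response, which is plausible but not documented for the adolescent CDLQI and high-baseline HADS subsets.

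The conclusion that the variance is wrong at x = n rests on the formula alone. The stated coverage losses rest on the assumed sizes and rates. For comparisons with placebo at 30/15, the loss exceeds 1 point only at the highest rates tried (0.95 versus 0.60, 1.6 points). The dose comparison can lose more, about 12 to 13 points in the single setting examined. The co-primary conclusions are unaffected.

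**What to change.** Add to SAP 5.2.1, beside the existing rule: when all subjects in a cell respond (x = n), replace the estimated proportion by (n + 0.5)/(n + 1) in the variance only. This mirrors the sponsor's own correction and makes the width independent of coding. In the settings examined, coverage was equal or higher. In the dose comparison it rose to 98.6%, which is somewhat conservative.

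The cost is one SAP clause and one line of code; no hypothesis test on the co-primary endpoints changes. It is best settled before unblinding, so that a 0 to 0 interval does not need a post hoc repair.

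The clause does not cure the rest of the small-sample undercoverage: roughly 90% to 93% remains in the affected placebo comparisons at 15/7. If that matters for these subsets, a score or exact-type interval could be specified for them instead.
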